4.4. Treatments

4.4.1. Treatments Administered

Fosfomycin is administered orally daily as one 3-gram single-dose sachet into 3-4 ounces of cool water. Levofloxacin is administered orally daily as one 750 mg tablet.

Alternative therapies cefixime (400 mg), amoxicillin-clavulanate (875/125 mg), and TMP-SMX (160/800 mg) are administered orally as one tablet once (cefixime) or twice (amoxicillin-clavulanate and TMP-SMX) daily.

Strategy 1 is defined as initial OR step-down therapy with fosfomycin 3 grams, oral powder, once daily and if indicated a subsequent investigator-directed adjustment to another adequate oral therapy.

Strategy 2 is defined as initial OR step-down therapy with levofloxacin 750 mg, oral tablet, once daily and if indicated a subsequent investigator-directed adjustment to another adequate oral therapy.

Initial therapy is defined as the first effective agent and step down therapy is defined as with prior effective agents. The dosing of oral therapy depends on CrCl.

4.4.2. Identity of Investigational Products

Fosfomycin is a synthetic, broad-spectrum, bactericidal antibiotic for oral administration. It is available as a single-dose sachet which contains white granules consisting of 5.631 grams of Fosfomycin tromethamine and the following inactive ingredients: mandarin flavor, orange flavor, saccharin, and sucrose.

Levofloxacin is a synthetic, broad-spectrum, antibacterial agent. Levofloxacin is a light yellowish-white to yellow-white crystal or crystalline powder with an empirical formula of $C_{18}H_{20}FN_3O_4 \bullet \frac{1}{2} H_2O$ and the molecular weight is 370.38. The 750 mg film-coated tablet (expressed in the anhydrous form) contains the following inactive ingredients: hypromellose, crospovidone, microcrystalline cellulose, magnesium stearate, polyethylene glycol, titanium dioxide, and polysorbate 80.

Cefixime is supplied as a 200 mg chewable tablet, 400 mg capsule, or tablet, or oral suspension (100 mg/ 5mL and 200 mg/5 mL) for oral administration.

Amoxicillin-clavulanate is supplied as a tablet in the following strength: 875mg/125mg. The 875mg/125mg film-coated tablet is a white-off-white capsule shaped tablet. Each tablet contains 875 mg amoxicillin anhydrous and 125 mg clavulanate acid for oral administration.

TMP-SMX is supplied as a tablet in the following strength: 160 mg/800 mg (double strength). The 160 mg/800 mg double strength (DS) tablet for oral administration contains 800 mg SMX and 160 mg TMP

4.4.3. Method of Assigning Subjects to Treatment Groups (Randomization)

Per ICH guideline E6: Good Clinical Practice, screening records will be kept at each site to document the reason why an individual was screened, but failed trial entry criteria. The reasons why individuals failed screening will be recorded in the Data Coordinating Center's (DCC's) AdvantageEDCSM (Electronic Data Capture) system.

Once consented and upon entry of demographic data and confirmation of eligibility for the trial, the subject was enrolled. Enrollment of subjects was done online using the enrollment module of AdvantageEDCSM. Subjects were randomized 1:1 to receive oral therapy from Strategy 1 or Strategy 2. Subjects were stratified by (1) pyelonephritis vs. other cUTIs and (2) participating site.

The list of randomized treatment assignments was prepared by statisticians at the DCC (The Emmes Company) and included in the enrollment module of its Internet Data Entry System (IDES). The IDES assigned each subject a treatment code and treatment assignment from the list after demographic and eligibility data had been entered.

4.4.4. Selection of Doses in the Study

The duration of oral study therapy (initial + investigator-directed adjustment if indicated) in each strategy is 5-7 days of any per protocol antibiotic to which the pathogen is susceptible such that the total duration of effective antibacterial therapy (including pre-study administration of oral therapy escalated to parenteral therapy or parenteral therapy alone) is 7 days.

In the US, a tromethamine salt of fosfomycin has been FDA-approved since 1996 as a single oral sachet weighing 3 grams for the treatment of uncomplicated UTIs.

Levofloxacin at 750 mg daily was selected for this study because it is FDA-approved for the treatment of cUTI and the current standard of care in the US. The 750-mg dose of levofloxacin is used because it may more effectively eradicate pathogens and prevent amplification of resistant clones.

A subject's treatment might also be adjusted to receive another FDA approved treatment for cUTI if the causative pathogen is not susceptible in vitro to the initial treatment or the subject develops an intolerance or allergy or the subject has an underlying condition posing an increased risk with the original therapy. Possible adjustments are:

- Levofloxacin 750 mg oral tablet once daily (Strategy 1 only)
- Fosfomycin 3 grams oral powder once daily (Strategy 2 only)
- Amoxicillin-clavulanate 875/125 mg oral tablet twice daily
- Cefixime 400 mg oral tablet once daily
- Trimethoprim-sulfamethoxazole (TMP-SMX) 160/800 mg double-strength oral tablet twice daily

These doses will be adjusted per subject depending on their Creatinine Clearance (CrCl) as described in Section 4.4.5.

4.4.5. Selection and Timing of Dose for Each Subject

Fosfomycin is administered orally as one 3-gram single-dose sachet into 3-4 ounces (1/2 cup) of cool water. If CrCl is <20 mL/min, fosfomycin should be taken as 3 grams every other day.

Levofloxacin 750 mg is administered orally as one tablet once daily with or without food for normal kidney function. If CrCl is 20-49 mL/min, 750 mg should be taken every other day. If on subsequent testing post-randomization, the CrCl <20 mL/min, the dose is 500 mg every other day.

Cefixime 400 mg is administered orally as one tablet or capsule once daily with or without food for normal kidney function. If CrCl is between 21 to 59 mL/min, 260 mg of oral suspension should be taken once daily. If on subsequent testing post-randomization CrCl is \leq 20 mL/min, 200 mg chewable tablet should be taken once daily.

Amoxicillin-clavulanate 875/125 mg is administered orally as one tablet twice daily ideally at the start of a meal for normal kidney function. If on subsequent testing post-randomization CrCl is between 10 and < 20 mL/min, 500/125 mg should be taken twice daily or if CrCl is < 10 mL/min, 500/125 mg should be taken once daily.

TMP-SMX 160/800 mg is administered orally as one double-strength tablet twice daily with or without food for normal kidney function. If on subsequent testing post-randomization CrCl is between 15 and <20 mL/min, one single-strength tablet (TMP-SMX 80/400 mg) should be taken twice daily. This treatment should not be given if CrCl is <15 mL/min.

4.4.6. Blinding

None; this is an open-label trial.

4.4.7. Prior and Concomitant Therapy

Medication history (concomitant medications) will include a review of all current medications and medications taken within 30 days before signing the informed consent form (ICF) through the TOC visit. Prescription and over-the-counter drugs will be included as well as herbals, vitamins, and supplements.

When co-administered with fosfomycin, metoclopramide lowers the serum concentration and urinary excretion of fosfomycin, with other drugs that increase gastrointestinal motility producing similar effects. Subjects should be counseled regarding this potential interaction and metoclopramide dosing should be separated by at least 3 hours from fosfomycin dosing.

Levofloxacin should be administered at least 2 hours before or 2 hours after antacids containing magnesium or aluminum, as well as sucralfate, metal cations (e.g., iron), multivitamins containing zinc, or didanosine chewable/buffered tablets.

4.4.8. Treatment Compliance

Subjects will be directly observed at the time of first dosing by a member of the clinical research team who is trained to administer the study drug. Administration will be documented on the source document and entered in the eCRF. A pill/sachet count will be performed.

4.5. Efficacy and Safety Variables

For the primary outcome, the frequency and proportion of subjects achieving treatment success at the TOC visit will be reported by treatment strategy. For the secondary and exploratory efficacy outcomes, the frequency and proportion of subjects achieving treatment success, clinical cure, microbiological success, and adjustment-free treatment success at TOC and EOT will be reported by treatment strategy and will be reported overall as well as stratified by subgroups including cUTI type, investigator-adjusted therapy, age group (<65, ≥65 years), BMI (<30, ≥30 kg/m²), sex, creatinine clearance (≥60 mL/min, <60 mL/min), indwelling urinary catheter, obstructive uropathy, diabetes, recurrent UTI status, number of days of antibiotics use (≤7, >7 days), and susceptibility to various pathogens at baseline. Note that subgroup analysis will be performed only for subgroups with total sample size above 10 subjects. Refer to Section 3.3 for definitions of treatment success, clinical cure, and microbiological success (cure).

95% confidence intervals (CIs) of frequencies of solicited and unsolicited AEs, SAEs and adverse events of special significance (AESIs) will be provided using the Wilson method.

Frequency and number of solicited AEs of grade 2 and above will be reported by treatment strategy, study day, and severity, and differences between treatment arms in frequency of grade 2 and above severity solicited AEs after the first dose of study drug will be tested using Fisher Exact Tests. For subjects receiving fosfomycin, frequency and number of each solicited adverse event of grade 2 and above severity occurring any time from date of first dose of fosfomycin in subjects receiving 2 or more doses until 2 days after last dose of fosfomycin will be tabulated. See Table 1 for schedule of study procedures.

Frequency and number of SAEs in subjects receiving at least two doses of fosfomycin during the trial will be tabulated.

All AEs will be graded for severity and relationship to study drug (see definitions below). AEs characterized as intermittent require documentation of onset and duration of each episode. The start and stop date of each reported AE will be recorded on the appropriate data collection form and eCRF.

Only Grade 2 and above AEs and SAEs will be reported. AESIs of any grade will be reported.

Severity of Event:

Solicited AEs will be assessed by the investigator using a protocol-defined grading system ([Table 3](#)). For unsolicited AEs, the following guidelines will be used to quantify severity:

- Mild (Grade 1): Events require minimal or no treatment; do not interfere with the subject's daily activities.
- Moderate (Grade 2): Events result in a low level of inconvenience or concern with therapeutic measures; may cause some interference with functioning and daily activities.
- Severe (Grade 3): Events interrupt the subject's daily activities and may require systemic drug therapy or other treatment; are usually incapacitating.

Changes in the severity of an AE should be documented to allow an assessment of the duration of the AE at each level of intensity to be performed.

5. SAMPLE SIZE CONSIDERATIONS

This is a Phase IV multicenter, open-label, randomized pragmatic superiority clinical trial comparing two strategies for step-down oral therapy for cUTI. The basic null hypothesis of this trial is:

H0: The probability of success (clinical cure and microbiological cure) at TOC is not conditional on the treatment strategy.

This hypothesis testing question will result in one of three statements regarding the results of this trial:

1. Strategy 1 is superior to Strategy 2.
2. Strategy 2 is superior to Strategy 1.
3. Evidence from the trial is insufficient to conclude that either strategy is superior.

The primary analysis will use the micro-ITT population, defined as all randomized subjects who have a positive baseline bacterial culture of urine. Subjects will not be excluded from this population based upon events that occurred post-randomization (e.g., loss to follow-up). An assumption of 92% micro-ITT eligibility is made for the sample size calculations. If 634 subjects are enrolled with 1:1 allocation, 291 subjects per arm would be expected to qualify for the micro-ITT population. Assuming a 10% difference in treatment success at TOC, with 80% success for one strategy and 70% success for the other strategy, there will be 80% power to reject the null hypothesis using a two sided ztest (without continuity correction), with a Type I error rate of 5%. These calculations assume an interim analysis after 40% of subjects have completed the study, with Type I error controlled using Lan DeMets with an O'Brien Fleming spending function. The specific success rates of 70% and 80% are based on a 10% clinically significant difference an approximate rate of success consistent with example calculations in the FDA guidance for cUTI studies. Sample size calculations were computed using PASS 2008 software. The calculations do not adjust for dropout, because analysis methods will include subjects that have dropped out early, assuming they meet micro-ITT criteria (Section 6.3.1).

If true success rates are instead 65% and 75%, there will be 75% power to conclude a difference in the strategies. If true success rates are 80% and 90%, there will be 92% power to conclude a difference.

However, this study was terminated early due to slow enrollment with only 62 subjects enrolled in the study. Only 48 out of the 62 subjects were eligible to be in the micro-ITT analysis population. Using the same assumptions of 10% difference in the treatment success, there was only a 12% power to reject the null hypothesis using a two sided z-test (without a continuity correction) with a Type I error rate of 5. Given this low power, the efficacy results should be interpreted with caution as to not make any conclusions regarding the superiority of either strategy.

6. GENERAL STATISTICAL CONSIDERATIONS

6.1. General Principles

All continuous variables will be summarized using the following descriptive statistics: n (non-missing sample size), mean, standard deviation, median, maximum and minimum. The frequency and percentages (based on the non-missing sample size) of observed levels will be reported for all categorical measures. In general, all data will be listed, sorted by treatment group, and subject, and when appropriate by time within subject. The listing of non-subject specific protocol deviation will be sorted by site, start date and deviation. All summary tables will be structured with a column for each treatment and will be annotated with the total population size relevant to that table/treatment.

6.2. Timing of Analyses

The final analysis described in this SAP will be performed after database lock.

6.3. Analysis Populations

The primary analysis will be performed using the micro-ITT population. Other analyses, as specified below, may use the complete cases (CC) at Test of Cure or End of Therapy (CC-TOC or CC-EOT) populations. Analyses of the micro-ITT population will include imputation for missing data (Section 8.4), while analyses of the CC populations will not contain missing data by design. Analysis of clinical cure will use the ITT analysis population and will include imputation for missing data. Analysis of clinical cure will be repeated to use all subjects in ITT with complete data. Analysis of unsolicited events will use the Fosfomycin safety analysis population while analysis of solicited events will use both the Safety and Fosfomycin Safety populations.

Reasons for exclusion from each analysis population are summarized in [Table 7](#) and shown by subject in [Listing 4](#). Excluded subjects might satisfy multiple criteria justifying their exclusion but will have only the first exclusion criteria met for a given population indicated in [Table 7](#) and [Listing 4](#). The reason indicated will be determined by the following rules in order.

ITT Analysis Exclusion Reasons:

- Subject not randomized

Micro-ITT Analysis Exclusion Reasons:

- Subject does not have a baseline culture from a urine sample taken prior to treatment with study drug
- Baseline culture is not positive for a uropathogen or is contaminated

CC-TOC Analysis Exclusion Reasons:

- Subject not in micro-ITT population
- Subject not treated with at least one dose of study product
- Early termination before TOC
- Missing urine culture or had a urine culture that was contaminated at TOC

CC-EOT Analysis Exclusion Reasons:

- Subject not in micro-ITT population

-
- Subject not treated with at least one dose of study product
 - Early termination before EOT
 - Missing urine culture or had a urine culture that was contaminated at EOT

Safety Analysis Exclusion Reasons:

- Subject not treated with at least one dose of study product

Fosfomycin Safety Analysis Exclusion Reasons:

- Subject not treated with at least two doses of Fosfomycin

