3.3. Study Definitions and Derived Variables

Clinical cure is defined as:

- Resolution of UTI symptoms from presentation (fever, hypothermia, chills or rigors or warmth, flank pain, flank tenderness, suprapubic pain, pelvic pain, suprapubic tenderness, nausea, vomiting, pain on urination, urinary frequency, urinary urgency)

AND

- No new UTI symptoms

AND

- Avoidance of parenteral antibiotic therapy, in or out of hospital, at any time after randomization **OR** oral antibiotic therapy different from per protocol

A subject will be considered a clinical failure if at least one of the above conditions is not met.

Microbiological success (Microbiologic cure) is defined as:

- Reduction of the pathogen found at presentation to $<10^4$ CFU/mL for non-catheter specimens or $<10^3$ for catheter specimens on urine culture.

Treatment success (composite cure) is defined as:

- Clinical cure and microbiological success.
- Treatment Success will be referred to as Composite Cure in manuscript TFLs.

Treatment Failure is defined as:

- A subject will be considered a treatment failure if the subject experiences clinical/microbiologic failure **OR** if the subject develops bacteremia with a uropathogen after randomization.

Adjustment-free treatment success is defined as:

- Treatment success without therapy adjustments.

Relapse infection is defined as:

- Recurrence of UTI symptoms between EOT and TOC.

End of Therapy (EOT) Visit is also referred to as Visit 3 in the protocol and will occur within 2 days of the completion of oral therapy. The window for this visit is Day 5-10 +2 days.

Test of Cure (TOC) Visit is the final visit for this study (Visit 4) and will be scheduled within the window of Day 21 + 7 days after randomization.

Day 1: is defined as the day of first dose for subjects who were treated with study product. For subjects not treated with study product, Day 1 will be defined as the day of randomization.

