4.3.3. Reasons for Withdrawal

Subject Withdrawal

A subject or a subject's LAR may voluntarily withdraw their consent for study participation at any time without penalty or loss of benefits to which they are otherwise entitled.

Subjects diagnosed with bacteremia with a uropathogen after randomization are considered treatment failures and will only be followed for safety and referred to standard of care for treatment.

The investigator may also discontinue a subject for other reasons; however, follow-up safety evaluations will be conducted if the subject/subject's LAR agrees.

If a subject withdraws or is discontinued before completion of the trial, the reason will be recorded in the electronic case report form (eCRF).

Additional reasons for withdrawal might include, but are not limited to, the following:

- Medical disease or condition, or new clinical finding(s) for which continued participation, in the opinion of the investigator or the patient's primary medical provider, might compromise the safety of the subject.
- Subject is lost to follow-up.
- Termination of the trial.

Study Drug Discontinuation

Subjects who discontinue study drug should remain in study and be assessed for safety and clinical/microbiological success per defined criteria. Discontinuation of study drug does not, per se, cause withdrawal from the trial nor by itself constitute treatment failure.

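### SAP 6.3 lists early termination and a missing or contaminated culture as complete-case exclusions with no exception for a determined failure, and SAP 8.4.1 gives such a subject no assured place in the primary datasets

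*SAP*

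**What the plan says.** **Who is a failure.** SAP 3.3 makes one unmet clinical condition enough for clinical failure, and states: "A subject will be considered a treatment failure if the subject experiences clinical/microbiologic failure". Bacteremia with a uropathogen after randomization also counts. One of the clinical conditions is "Avoidance of parenteral antibiotic therapy, in or out of hospital, at any time after randomization". A subject can therefore be a determined composite failure with no urine culture at the visit. Under SAP 4.3.3, subjects with bacteremia "are considered treatment failures and will only be followed for safety".

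**Who is a complete case.** SAP 6.3 gives these CC-TOC exclusion reasons: not in micro-ITT, not dosed, "Early termination before TOC", and "Missing urine culture or had a urine culture that was contaminated at TOC". CC-EOT has the parallel list. SAP 6.3.3 defines the same populations differently, as micro-ITT subjects with at least one dose and a non-missing treatment success value. SAP 8.2.2 and 8.3 also speak of no missing values.

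**Who is imputed.** SAP 6.3.2 and 8.4.1 impute only missing values. SAP 6.3.2 also says that post-randomization events do not remove anyone from micro-ITT. The 8.4.1 pseudo-code runs each imputation on the CC-TOC subjects plus one subject outside CC-TOC. It then forms the twenty completed datasets by merging the imputed rows with the CC-TOC rows.

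**The concern.** CC-TOC looks like a sensitivity population, but in 8.4.1 it also decides which rows enter the primary analysis. If the 6.3 list is applied as written, a subject known to have failed, but who left early or has no usable TOC culture, falls outside CC-TOC. The pseudo-code then has no rule that keeps that subject in the data as a failure.

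Two programmers working from the same SAP could then report different primary estimates. The affected arm's success rate would be overstated, and the same subjects would also be missing from the complete-case check. The effect on the between-arm difference depends on imbalance: it can go either way, is small if balanced, and is zero if there are no such subjects. SAP 8.4.1 fixes seeds and variable order so that results can be replicated exactly, which makes it odd to leave open which subjects are carried as observed.

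**Working it through.** **1. Is the 6.3 list a rule or a set of labels?**

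- For labels: SAP 6.3 says "The reason indicated will be determined by the following rules in order". The Table 7 implementation note says the SAP text sets the priority for assigning reasons. The Table 21 note lets the complete-case N vary with which endpoint is missing. The list also has no reason for a missing symptom assessment, so it cannot define the population alone.
- For a rule: SAP 6.3 also says "Excluded subjects might satisfy multiple criteria justifying their exclusion". Listing 4 wants its reasons to match the SAP text on who is excluded, and its footnote provides for available data having been removed.
- No sentence ranks 6.3 against 6.3.3. The only softening in 6.3.3 is a review of exclusions for contaminated cultures, with no rule attached. The Table 26 note adds a third wording: visit completed, or composite not missing.

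**2. What the code does with a determined failure outside CC-TOC.** PROC MI fills missing values only. An observed 0 stays 0 if the row is processed at all. But only subjects needing imputation are indexed, and only CC-TOC rows are merged back. So the row is either (a) omitted, against 6.3.2, or (b) imputed, if the derivation has first set the composite to missing. In case (b) the model uses strategy and baseline variables only, so the observed failure does not inform the value.

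**3. What remains if 6.3.3 governs.**

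- SAP 6.3.3 still requires a dose. An untreated micro-ITT subject with a determined composite is outside CC-TOC and has no row in the completed datasets. The SAP foresees untreated subjects ("For subjects not treated with study product, Day 1 will be defined as the day of randomization"), as does Protocol 5.3.5.
- A determined composite failure with no culture is in CC-TOC but lacks microbiological success. The code indexes only subjects whose treatment success is imputed, so microbiological success stays missing, although 6.3.2 and Table 20 say it is imputed.

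**4. Size.** Inputs: 48 in micro-ITT, and 80% vs 70% success (SAP 5). The split is not given; 24 per arm is assumed. These inputs reproduce the SAP's own 12% power: with pooled SE under the null √(2 × 0.75 × 0.25/24) = 0.125 and unpooled SE √(0.8 × 0.2/24 + 0.7 × 0.3/24) = 0.1242, power = Φ((0.10 − 1.96 × 0.125)/0.1242) = 12.1%.

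Let p be the arm's rate with failures scored 0, and k the determined failures removed. Omitting them, or imputing them at the mean of the rest, gives p·n/(n − k).

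| n | k | p = 70% | p = 80% |
|---|---|---|---|
| 24 | 1 | 73.04 (+3.04) | 83.48 (+3.48) |
| 24 | 2 | +6.36 | +7.27 |
| 20 | 1 | +3.68 | +4.21 |
| 28 | 1 | +2.59 | +2.96 |

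Difference, 80% vs 70%, 24 per arm:

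- none affected: 10.0 points
- one in the higher-rate arm: 83.48 − 70 = 13.5
- one in the lower-rate arm: 80 − 73.04 = 7.0
- one in each: 83.48 − 73.04 = 10.4

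95% Wald half-width: 1.96 × 0.1242 = 24.3 points (24.4 to 25.0 for a 20/28 split either way).

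**5. Simulation of 8.4.1** (24 per arm, 75% success among the rest, 20 imputations, composite of the determined failures set to missing first). Those subjects received a mean value of 0.74-0.75. With two in one arm and none in the other, the difference was −5.8 points with failures kept at 0, +0.3 when imputed and +0.4 when omitted. The shift of 6.1 agrees with 0.75 × 2/24 = 6.25 points. Single draws have an SD of about 0.5, so closeness to the mean holds on average only.

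**The case against.** A reader might infer that the primary imputation overwrites known failures with near-average values. The documents do not support that. SAP 6.3.2 and 8.4.1 impute missing endpoints only, and no passage tells the programmer to blank a determined 0. That step would have to be added in the derivation. This objection stands in full, and it makes omission of the row the more direct route to error.

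The label reading is also the better one: most of the relevant text favours it, and under it a determined failure stays in CC-TOC as a 0. It is not conclusive, because 6.3 calls its items exclusion criteria and Listing 4 treats them as such.

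A reader might further infer that bacteremia automatically triggers the early-termination exclusion. It need not. SAP 7.1 names bacteremia in a paragraph covering both early termination and treatment discontinuation, Listing 1 separates the two, and Protocol 5.3.4 defines early termination as ceasing participation before TOC. A subject in safety follow-up has not necessarily ceased.

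On materiality, untreated subjects should be few, since Protocol Visit 01 requires dosing on the day of randomization. Cultures are requested at failure, EOT and early termination. The grids in Tables 24 and 25 bracket the result, although no cell keeps determined failures at 0 while imputing only the undetermined. SAP 5 and 8.1.1 already call for caution. All of this lowers the stakes but does not settle which rows belong in the datasets.

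**Conclusion.** The point holds as an unresolved inconsistency, not as a demonstrated bias. SAP 6.3, read literally, excludes determined failures that 6.3.3 keeps, and 8.4.1 turns complete-case membership into the rule for assembling the primary micro-ITT datasets. If the literal reading were programmed, each such subject would raise its arm's rate by about 3.0-3.5 points (24 per arm, 70-80% success; 2.6-4.2 points with 28 to 20 per arm), against a half-width of about 24 points. The arm split and success rates are assumptions, and the number of such subjects is unknown and may be zero. The two gaps in section 3 of the working remain even if 6.3.3 governs; the first is likely to concern few subjects, and the second touches microbiological success, not the primary composite. Severity: minor to should-fix.

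**What to change.** 1. In SAP 6.3, state that the early-termination and culture reasons are labels that apply only when the composite is undetermined under 3.3, so that the list and Listing 4 agree with 6.3.3.
2. In SAP 8.4.1, impute only undetermined values, separately for each endpoint. Merge them with all micro-ITT subjects whose value is determined, treated or not, instead of with CC-TOC rows only.
3. In the derivation, set composite cure to 0 at a visit whenever an observed component already decides it under the SAP's own definitions.

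Whether symptoms at EOT followed by early termination decide the TOC composite is a separate endpoint question and is not part of this change.

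The cost is a few sentences and a few lines of code, with no new data. Compared with the literal reading, an affected arm's reported rate falls by about 3 points per such subject.
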